7. STATISTICAL METHODOLOGY AND STATISTICAL ANALYSES

7.1 STATISTICAL METHODS

Bioequivalence of pharmacokinetic parameters is determined by obtaining a 90% confidence interval of the mean difference between dosing groups, using the analysis of variance (ANOVA) model of log-transformed data.

For statistical analysis, the analysis of variance (ANOVA) model of SAS version 9.4 software (SAS Institute Inc.) is used, and Phoenix WinNonlin 8.0 (CERTARA USA Inc.) is used to calculate pharmacokinetic parameters from the blood concentrations.

In general, continuous data presents descriptive statistics (N, Mean, Standard Deviation, Median, Minimum, Maximum), and categorical data presents frequency (n) and percentage (%). Descriptive statistics for continuous data are presented to the second decimal place, the ratio (%) of categorical data to the first decimal place, and p-value is rounded to the fourth decimal place. At this time, if the p-value is less than 0.0001, it is presented as <0.0001. All verification is conducted at the significance level of 5%.

Blood concentration values are indicated with 3 significant digits, and basic statistics of blood concentration values are presented to the third decimal place. Pharmacokinetic parameters and their descriptive statistics are presented to the third decimal place, the geometric average ratio of the test drug to the reference drug is presented to the fourth decimal place (%Ratio is 2 decimal places), the 90% CI for the geometric mean ratio is presented up to 2 decimal places when expressed as a percentage of 4 decimal places, and Intra CV is presented to the first decimal place.

Detail contents for each parameter is presented in mock-ups of the Appendix.

7.2 STATISTICAL ANALYSIS

Randomization, demographic information, medical history, physical examination, vital signs, clinical laboratory test, pregnancy test, IMP administration, 12-lead ECG, prior/ concomitant medications, adverse events, Study Conclusion, Pharmacokinetic Profile, blood concentration, pharmacokinetic parameters are presented as Listing for the demographic assessment group. Detail contents for each variable is presented in mock-ups of the Appendix.

7.2.1 Study Disposition

List the study participation status information (informed consent signed date, completion status of BE study (study completion, dropout), dropout reason) for the subjects who participated in BE study and who were assigned randomization number. In addition, for all subjects participating in BE study, the summarized number of subjects based on the progress of clinical study (screening participants, screening failed participants, stand-by participants, replaced participants, dropout participants, study completed participants, demographic set, safety set, reasons for exclusion of safety set, pharmacokinetic set, reasons for exclusion of pharmacokinetic set) are presented.

7.2.2 Demographic Characteristics

The population for demographic analysis is demographic assessment group.

- Descriptive statistics per each sequence group like mean, standard deviation, etc. are analyzed for demographic information such as gender, age, height, weight, and BMI.

7.2.3 Pharmacokinetic Analysis

The population for pharmacokinetic analysis is pharmacokinetics assessment group.

AUC_{last} and C_{max} , AUC_{inf} (if data allows to calculate), $t_{1/2}$, converted to natural logs are analyzed using an analysis of variance (ANOVA) model having sequence group, subject (sequence group), period, and dosing group effects. In principle, analysis of variance shall be used at α (significance level) = 0.05. The mean square error (MSE) is then used for the %CV calculation.

Using the ANOVA results, the point estimate of the mean difference (T-R) and the corresponding 90% confidence interval are calculated, and they are indexed to calculate the point estimate of the geometric mean ratio (T/R) and the 90% confidence interval.

T_{max} presents the median of the reference drug and the test drug, and p-value is calculated through the Wilcoxon signed-rank test.

Pharmacokinetics parameters are summarized and listed according to the dosing group.

PK parameter	Summary statistics
AUC_{last} , C_{max} , AUC_{inf} , T_{max} , $t_{1/2}$, AUC_{last}/AUC_{inf}	N, Arithmetic Mean, Standard Deviation, Median, Minimum, Maximum, Geometric Mean, Geometric Coefficient of Variation

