Participant identifier & Assignment to treatment sequence	
For Part 1 (Fasted state) and Part 2 (Fed state), screening number in the form of SXXX (e.g. 'S301, S302, S303 ...' if it is for Part 1 and 'S401, S402, S403 ...' if it is for Part 2) is given to the applicants who visited the Clinical Facility and agreed the informed consent in writing. The screening number will be used to identify the participants for the whole duration of the bioequivalence study.
 
One day (Day -1) prior to administration of study intervention of Period 1, each participant is given a participant number according to the order of obtainment of the Informed Consent and the Sequence is randomly assigned to each of Part 1 (Fasted state) and Part 2 (Fed state). Randomization is done using Excel or SAS programs, and a total of 82 participants (Part 1: 48 participants, Part 2: 34 participants) are randomly assigned to 2 Sequences (1 or 2) with 24 participants per Sequence in Part 1 and 2 Sequences (1 or 2) with 17 participants per Sequence in Part 2 in a 1:1 ratio.
 
Randomization number is given to the 48 participants if it is Part 1 (Fasted state) and to the 34 participants if it is Part 2, excluding the stand-by participants (waiting list), who satisfied the screening, inclusion/exclusion criteria and clinical laboratory tests. The randomization number is the number of the administration order of participants and its form is R1YY (e.g., R101, R102, R103, ..., R148) if it is Part 1 (Fasted state) and R2YY (e.g., R201, R202, R203, ..., R234) if it is Part 2 (Fed state). Participants who have been assigned a randomization number but dropped out before the first administration of Period 1 can be replaced with stand-by participants. When the participant is replaced, the stand-by participant will be assigned the drop-out's randomization number. However, participants will not be replaced after the first administration of Period 1.

--	--

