9.4.3 Other Analyses

9.4.3.1 Analysis of Primary Endpoints

Primary Variables: AUC_{last} and C_{max} of metformin

- An analysis of variance (ANOVA) model will be fitted for the log-transformed PK parameters C_{max} and AUC_{last} based on the PK analysis set. The model will include treatment, period, sequence, and participant within sequence as fixed effects. Treatment differences on the log scale will be estimated for C_{max} and AUC_{last} together with their 90% CIs. Point estimates and CIs will be back-transformed to the original scale for the comparisons.

The comparison will be the test treatment (Glucophage® XR Reduced Mass tablet) vs the reference treatment (Glucophage® XR tablet) under fasting conditions in Part 1, and under fed conditions in Part 2. The null hypothesis for non-bioequivalence will be rejected if the 90% CI for the ratio of the GeoMean lies within the interval 0.8000 to 1.2500 for all primary pharmacokinetic parameters.

The primary endpoints will be descriptively analyzed and graphical displays will be prepared. PK analyses will be specified in the Integrated Analysis Plan finalized before database lock.

In principle, analysis of variance shall be used at α (significance level) = 0.05.

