2.2 STUDY DESIGN

This bioequivalence study is divided into two parts according to the method of administration of the Investigational Medicinal Products (IMPs): Part 1 (Fasted state) and Part 2 (Fed state).

Each part of the study is performed by an open label, randomized, 2-period, 2-sequence, single oral dose and crossover design.

A detailed description of the study design is specified in Table of Contents 4 of the BE Study Protocol.

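### The Tmax test ignores period and sequence and the SAP text plans no interval for the difference; if a period effect exists the test becomes conservative and loses power

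*SAP*

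**What the plan says.** SAP 2.2 describes the design: "Each part of the study is performed by an open label, randomized, 2-period, 2-sequence, single oral dose and crossover design". Protocol 6.3.1 allocates "24 participants per Sequence in Part 1 and 2 Sequences (1 or 2) with 17 participants per Sequence in Part 2 in a 1:1 ratio".

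For AUClast, Cmax, AUCinf and half-life, SAP 7.2.3 uses logged values in an "analysis of variance (ANOVA) model having sequence group, subject (sequence group), period, and dosing group effects", and then: "Using the ANOVA results, the point estimate of the mean difference (T-R) and the corresponding 90% confidence interval are calculated". Protocol 9.4.3.1 sets the same structure for the primary parameters: "The model will include treatment, period, sequence, and participant within sequence as fixed effects".

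Tmax is handled differently in the same SAP section: a median is given for each drug, and the "p-value is calculated through the Wilcoxon signed-rank test". The summary table there adds only statistics by treatment: "N, Arithmetic Mean, Standard Deviation, Median, Minimum, Maximum, Geometric Mean, Geometric Coefficient of Variation". SAP section 8 lists Table 11 for the non-parametric analysis, but its layout is not among the documents.

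Tmax is a secondary endpoint. Protocol 9.4.3.2 plans descriptive analysis for the secondary endpoints, and SAP 3.2 leaves Tmax out of the bioequivalence rule.

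**The concern.** Every other PK parameter that is tested gets a model matching the crossover, plus an estimate and a 90% CI. Tmax gets a paired test that treats the two periods as interchangeable. Any general change in Tmax from Period 1 to Period 2 then enters the test-minus-reference differences with opposite sign in the two sequences.

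The p-value addresses only the hypothesis of no difference. It does not say how large a timing shift is compatible with the data. With 22 evaluable participants planned in the fed part, a non-significant result is weak evidence of similar timing. For a reformulated extended-release tablet, the size of the shift is the useful result. At stake is the quality of one secondary result, not the bioequivalence conclusion.

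**Working it through.** **Sample sizes.** The documents state no power for Tmax, so the only figures to reproduce are the evaluable numbers in Protocol 9.2.2. Exact two one-sided test power (ratio 0.95, one-sided alpha 0.05) gives N = 38 at CV 25% (power 90.9%) and N = 22 at CV 18.7% (power 90.6%). Drop-out inflation gives 38/0.80 = 47.5, so 48, and 22/0.65 = 33.8, so 34. All agree with the plan. The Tmax check uses 19+19 (fasted) and 11+11 (fed).

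**Algebra.** Let tau be the true T-R difference, pi the Period 2 minus Period 1 effect, n1 and n2 the completers in RT and TR, and N = n1 + n2. T-R has expectation tau + pi in RT and tau - pi in TR. Pooled over sequences:

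- mean = tau + pi(n1 - n2)/N
- variance = within-sequence variance + pi²[1 - ((n1 - n2)/N)²]

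With equal sequences the mean is unaffected but the spread grows. At a within-participant SD of 0.7 h, the within-sequence variance of T-R is 2 x 0.49 = 0.98, an SD of 0.99 h. The pooled SD becomes √(0.98 + 0.0625) = 1.02 h at pi = 0.25 h, √(0.98 + 0.25) = 1.11 h at 0.5 h, and √(0.98 + 1) = 1.41 h at 1.0 h. The test treats this extra spread as noise.

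**Power by simulation.** Tmax was placed on each part's protocol sampling grid. Assumed, not in the documents: SDs of 0.7 h between and within participants, a true shift of 0.6 h, and the period effects. The total SD is √(0.49 + 0.49) = 0.99 h, in line with the 1.0 h and 1.1 h cited in Protocol 4.1.2 for 750 mg XR. Tests are two-sided at 5%.

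| Period effect | Fasted 19+19: signed-rank | Fasted: period-adjusted | Fed 11+11: signed-rank | Fed: period-adjusted |
|---|---|---|---|---|
| 0 h | 0.92 | 0.91 | 0.73 | 0.71 |
| 0.5 h | 0.89 | 0.93 | 0.64 | 0.70 |
| 1.0 h | 0.73 | 0.91 | 0.40 | 0.69 |

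The losses are 0.93 - 0.89 = 4 and 0.70 - 0.64 = 6 points at 0.5 h, and 0.91 - 0.73 = 18 and 0.69 - 0.40 = 29 points at 1.0 h. At 0.25 h the tests are level: 0.90 against 0.91 fasted, 0.71 against 0.70 fed. Repeat runs move single cells by up to about 3 points.

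A second set of assumptions (total SD 1.0 h fasted and 1.1 h fed, correlation 0.5, true shift 0.5 h) gives the same pattern. At 0 / 0.5 / 1.0 h, signed-rank power is 78 / 73 / 54% fasted and 47 / 41 / 25% fed. The period-adjusted test gives 78 / 79 / 79% and 48 / 48 / 47%.

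**Unequal completers.** For a fed split of 14+8 the location shift is 0.5 x 6/22 = 0.14 h, or 1.0 x 6/22 = 0.27 h. The simulated Hodges-Lehmann estimate from T-R differences was off by about 0.14 h and 0.29 h; the period-adjusted one was unbiased. If drop-out is unrelated to sequence, 14+8 or worse among 22 fed completers has hypergeometric probability 0.07.

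**Type I error averaged over such drop-out** (SDs of 0.7 h), at period effects 0 / 0.25 / 0.5 / 1.0 h: 4.8 / 4.3 / 3.3 / 1.2% fasted and 5.0 / 4.7 / 3.6 / 1.9% fed. The test is conservative.

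**The case against.** The strongest reply is that nothing depends on this p-value. Tmax is outside the bioequivalence rule, the protocol plans it descriptively, and no margin or power is claimed for it. That stands, and it limits the point to an optional improvement.

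The second reply is that a large period effect is unlikely. Dosing time, fasting, meals, water and sampling are the same in both periods, and the washout is at least 7 days against a stated half-life of about 3.27 h. A 1.0 h effect is about one full cited SD of Tmax. This stands too: 1.0 h is an extreme case, and at 0.25 h nothing is lost.

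A reader might infer that the test is biased or likely to report a spurious shift, because drop-outs of about 20% and 35% are expected, are excluded, and are not replaced after dosing. The documents do not support that. Some imbalance is likely, but the shift is conditional on the realised split and averages to zero if drop-out is unrelated to sequence. Clear inflation appeared at a fasted split of 24+14 (7.1% and 12.8% at 0.5 and 1.0 h, second set of assumptions). That split needs all 10 drop-outs in one sequence, a probability of 0.0006. At 22+16 the rates were 4.4% and 3.2%. Even 0.29 h is less than one sampling interval near the expected Tmax (0.5 to 1 h).

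Two further limits hold. The SAP defers detail to mock-ups that are not available, so an interval is absent from the SAP text but could appear in Table 11. Planned individual and mean concentration curves would also show a timing shift.

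None of this supplies a reason to prefer the signed-rank test, or a planned estimate of the difference.

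**Conclusion.** The point holds as a low-severity mismatch between test and design. The signed-rank test disregards period and sequence, and the SAP text gives no estimated Tmax difference or interval. The missing interval matters whether or not there is a period effect. The power loss needs one, and the documents give no value for it. The loss figures also rest on the assumed SDs and true shift; the cited Tmax SDs are total SDs at 750 mg, not within-participant values at 500 mg. The evidence supports a conservative test that loses power, not a test with inflated error on average. A material location shift needs marked imbalance together with a large period effect. The AUClast and Cmax conclusion and the sample size are unaffected.

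**What to change.** In SAP 7.2.3 and Table 11, replace the signed-rank test with the Wilcoxon rank-sum test on half the within-participant period differences (Period 1 minus Period 2), comparing sequences RT and TR. Report the Hodges-Lehmann median T-R difference, taken as TR minus RT on that scale, with its 90% CI, separately for the fasted and fed parts.

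This takes one SAP sentence, one table layout and a standard procedure; no new data are needed. With balanced sequences and no period effect, the cost is up to about 2 to 3 power points.

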7.2.4 Safety Analysis

The population for safety analysis is the safety assessment group.

- For all adverse events after administration, System Organ Class (SOC) and Preferred Term (PT) classified using MedDRA [V23.0 or latest] are summarized for the number of subjects per dosing group, number of occurrences, and ratio (percentage). Adverse events having causal relationship with Study Interventions and adverse events not having causal relationship with Study Interventions are also presented.
- Using the WHO ATC [2020 or latest] classification system, concomitant drugs are summarized and presented for the number of subjects per dosing group, number of occurrence, and ratio (percentage) by ATC Level 1 and Level 3. The concomitant drug dosing group is based on the start date of the concomitant drug administration, and the concomitant drug dosing group taken during the wash out period is included as a group of Study Interventions dosing taken at the prior period.
- The data of vital sign test is presented by calculating the descriptive statistics of each test item for each dosing group at each evaluation time point.
- The data of clinical laboratory test is presented by calculating the descriptive statistics of each test item for each dosing group at each evaluation time point. Depending on whether the reference value is deviated or not, the meaning is assessed as normal, abnormal/no clinical significance (Abnormal/NCS) and

abnormal/clinical significance (Abnormal/CS). Percentage per each dosing group is presented.

- The data of physical examination is assessed as normal, abnormal/no clinical significance (NCS) and abnormal/clinical significance (CS) according to the result of each test item at each evaluation time point. Percentage per each dosing group is presented.
- The data of 12-lead ECG is assessed as normal, abnormal/no clinical significance (Abnormal/NCS) and abnormal/clinical significance (Abnormal/CS) according to the result of each test item at each evaluation time point. Percentage per each dosing group is presented.
- The data of Blood Sugar Test is presented by calculating the descriptive statistics of each test item for each dosing group at each evaluation time point.

7.2.5 Interim Analysis

Interim analysis of data will not be performed.

8. LIST OF STATISTICAL APPENDICES

The numbers assigned to tables, lists and graphs were assigned during the analysis stage, and the final number will be assigned when the result report is generated. TLF is provided separately fasted and fed.

List of Tables

Table 1	Summary of Disposition
Table 2.1	Adverse events after dosing
Table 2.2	Adverse events after dosing related to the study drug
Table 2.3	Adverse events after dosing not related to the study drug
Table 2.4	Non-serious TEAEs by SOC and PT at a Frequency Threshold of 5%
Table 3	Concomitant Medication
Table 4	Summary Statistics of demographic characteristics
Table 5	Summary Statistics of Vital signs
Table 6.1	Summary Statistics of Laboratory tests
Table 6.2	Summary of Clinical significance of Laboratory tests
Table 7.1	Summary Statistics of 12-lead ECGs

List of Tables

Table 7.2 Summary of Clinical significance of 12-lead ECGs

Table 8 Summary of Clinical significance of Physical examination

Table 9 Summary Statistics of Blood Sugar Test(BST)

Table 10 Summary of Parametric statistical analysis of plasma metformin pharmacokinetic variables

Table 11 Summary of Non-parametric statistical analysis of plasma metformin pharmacokinetic variable

List of Figures

Figure 1 Plasma metformin arithmetic and geometric mean concentrations

Figure 2 Combined individual plasma metformin concentrations

Figure 3 Individual plasma metformin concentrations

Listings

Listing 1 Randomization and dosing

Listing 2 Demography and Anthropometry

Listing 3 Medical History

Listing 4 Physical examination

Listing 5 Vital Signs

Listing 6 Full blood count for subjects with abnormal values

Listing 7 Clinical chemistry for subjects with abnormal values

Listing 8 Urinalysis for subjects with abnormal values by Investigators Assessment

Listing 9 Pregnancy Test

Listing 10 Electrocardiography

Listing 11 Dosing

Listing 12 Prior/Concomitant medication

Listing 13 Adverse Events

Listing 14 Disposition

Listing 15 Blood sampling times and deviations

Listing 16 Blood Sugar Test(BST)

Listing 17 Plasma metformin concentrations (summary results)

Listing 18 Plasma metformin pharmacokinetic variables (summary results)

